7.1.2 Serious Adverse Event

The Investigator will determine the seriousness of an AE based on the following. An AE is considered a SAE if at least one (1) of the following conditions applies:

- *Death*: An AE that results in death is any patient death within 30 days of the last dose of study drug administration. The cause of death or AE that resulted in a fatal outcome is the SAE.
- *Life-threatening AE*: An AE that places the patient, in the view of the Investigator or Takeda, at immediate risk of death from the event as it occurred (ie, this does not include an event that had it occurred in a more severe form, might have caused death).
- *Results in a persistent or significant incapacity or substantial disruption of the ability to conduct normal life functions* is defined as any substantial disruption of a person's ability to conduct normal life functions.
- *Inpatient hospitalization or prolongation of existing hospitalization*: Hospitalization refers to admission of a patient into a hospital for any length of time.

- *A congenital anomaly/birth defect:* A fixed, permanent impairment established at or before birth.
- *Overdose:* Any AE associated with an overdose of study drug. An overdose of study drug is defined as an occurrence of administered dose exceeding that which is prescribed by the investigator per protocol.
- *Important medical event:* Medical and scientific judgment should be exercised in determining whether an event is an important medical event. An important medical event may not result in death, be life-threatening, or require hospitalization. However, if it is determined that the event may jeopardize the patient and/or may require intervention to prevent one of the other outcomes listed in the definition above, the important medical events should be reported as serious. Examples of such events are intensive treatment in an emergency room or at home for allergic bronchospasm, blood dyscrasias, or convulsions that do not result in hospitalization; or the development of drug dependency or drug abuse.

AEs reported from clinical trials that require hospitalization or prolongation of hospitalization are considered serious. Any initial admission (even if less than 24 hours) to a health care facility meets these criteria. Adverse events that require emergency room care that do not result in hospital admission are not SAEs unless assessed by the investigator to be an important medical event. Hospitalization does not include the following:

- Hospice facilities
- Respite care
- Skilled nursing facilities
- Nursing homes
- Routine emergency room admissions
- Same day surgeries (as outpatient/same day/ambulatory procedure)

Hospitalization or prolongation of hospitalization in the absence of a precipitating AE is not in itself a SAE. Examples include:

- Social admission (eg, patient has no place to sleep)
- Protocol-specified admission during a clinical trial (eg, for a procedure required by the trial protocol)
- Optional admission not associated with a precipitating AE (eg, for elective cosmetic surgery that was planned prior to study enrollment [appropriate documentation is required for these cases])

7.1.3 Abnormal Test Findings

Test results meeting \geq grade 3 CTCAE v4 criteria will be reported to the principal investigator and will be reported as adverse events.

7.2 Adverse Reactions for Ponatinib

The following adverse events and reactions described in this section can be found described in further detail in the prescribing information for ponatinib.

- Vascular Occlusion
- Heart Failure
- Hepatotoxicity
- Hypertension
- Pancreatitis
- Neuropathy
- Ocular Toxicity
- Hemorrhage
- Fluid Retention
- Cardiac Arrhythmias
- Myelosuppression

The adverse events described in this section were identified in a single-arm, open-label, international, multicenter trial in 449 patients with CML or Ph+ALL who disease was considered to be resistant or intolerant to prior tyrosine kinase inhibitor (TKI) therapy including those with the BCR-ABL T315I mutation. All patients received a starting dose of 45 mg ponatinib once daily. At the time of analysis, the median duration of treatment with ponatinib was 337 days in patients with CP-CML, 362 days in patients with AP-CML, 89 days in patients with BP-CML, and 81 days in patients with Ph+ ALL. The median dose intensity was 37 mg or 83% of the expected 45 mg dose. The events of arterial ischemia, cardiac failure, and peripheral neuropathy reported in the tables below include data from an additional 13 months of follow-up (median duration of treatment CP-CML: 672 days, AP-CML: 590 days, BP-CML: 89 days, Ph+ ALL: 81 days).

Adverse reactions reported in more than 10% of all patients treated with ponatinib in this trial are presented in the table below. Overall, the most common non-hematologic adverse reactions (\geq 20%) were hypertension, rash, abdominal pain, fatigue, headache, dry skin, constipation, arthralgia, nausea, and pyrexia.

Adverse Reactions Occurring in >10% of Patients, Any Group

	CP-CML (N=270)		AP-CML (N=85)		BP-CML (N=62)		Ph+ ALL (N=32)	
System Organ Class	Any Grade (%)	CTCAE Grade 3 / 4 (%)	Any Grade (%)	CTCAE Grade 3 / 4 (%)	Any Grade (%)	CTCAE Grade 3 / 4 (%)	Any Grade (%)	CTCAE Grade 3 / 4 (%)
Cardiac or Vascular disorders								
Hypertension (a)	68	39	71	36	65	26	53	31
Arterial ischemia (b)*	20	11	19	9	10	5	3	0
Cardiac Failure (c)*	7	4	6	4	15	8	6	3
Gastrointestinal disorders								
Abdominal pain (d)	49	10	40	8	34	6	44	6
Constipation	37	2	24	2	26	0	47	3
Nausea	23	1	27	0	32	2	22	0
Diarrhea	16	1	26	0	18	3	13	3
Vomiting	13	2	24	0	23	2	22	0
Oral mucositis (e)	10	1	15	1	23	0	9	3

	CP-CML (N=270)		AP-CML (N=85)		BP-CML (N=62)		Ph+ ALL (N=32)	
System Organ Class	Any Grade (%)	CTCAE Grade 3 / 4 (%)	Any Grade (%)	CTCAE Grade 3 / 4 (%)	Any Grade (%)	CTCAE Grade 3 / 4 (%)	Any Grade (%)	CTCAE Grade 3 / 4 (%)
GI hemorrhage (f)	2	<1	8	1	11	5	9	6
Blood and lymphatic system disorders								
Febrile neutropenia	1	<1	4	4	11	11	25	25
Infections and infestations								
Sepsis	1	1	5	5	8	8	22	22
Pneumonia	3	2	11	9	13	11	9	3
Urinary tract infection	7	1	12	1	0	0	9	0
Upper respiratory tract infection	11	1	8	0	11	2	0	0
Nasopharyngitis	9	0	12	0	3	0	3	0
Cellulitis	2	1	4	2	11	3	0	0
Nervous system disorders								
Headache	39	3	28	0	31	3	25	0
Peripheral neuropathy (g)*	16	2	11	1	8	0	6	0
Dizziness	11	0	5	0	5	0	3	0
Respiratory, thoracic, and mediastinal disorders								
Pleural effusion	3	1	11	2	13	0	19	3
Cough	12	0	17	0	18	0	6	0
Dyspnea	11	2	15	2	21	7	6	0
Skin and subcutaneous tissue disorders								
Rash and related conditions	54	5	48	8	39	5	34	6
Dry skin	39	2	27	1	24	2	25	0
Musculoskeletal and connective tissue disorders								
Arthralgia	26	2	31	1	19	0	13	0
Myalgia	22	1	20	0	16	0	6	0
Pain in extremity	17	2	17	0	13	0	9	0
Back pain	15	1	11	2	16	2	13	0
Muscle spasms	12	0	5	0	5	0	13	0
Bone pain	12	<1	12	1	11	3	9	3
General disorders and administration site conditions								
Fatigue or asthenia	39	3	36	6	35	5	31	3
Pyrexia	23	1	31	5	32	3	25	0
Edema, peripheral	13	<1	19	0	13	0	22	0
	CP-CML (N=270)		AP-CML (N=85)		BP-CML (N=62)		Ph+ ALL (N=32)	
Pain	8	<1	7	0	16	3	6	3
Chills	7	0	11	0	13	2	9	0
Metabolism and nutrition disorders								
Decreased appetite	8	<1	12	1	8	0	31	0
Investigations								
Weight decreased	6	<1	7	0	5	0	13	0

	CP-CML (N=270)		AP-CML (N=85)		BP-CML (N=62)		Ph+ ALL (N=32)	
System Organ Class	Any Grade (%)	CTCAE Grade 3 / 4 (%)	Any Grade (%)	CTCAE Grade 3 / 4 (%)	Any Grade (%)	CTCAE Grade 3 / 4 (%)	Any Grade (%)	CTCAE Grade 3 / 4 (%)
Psychiatric disorders								
Insomnia	7	0	12	0	8	0	9	0

Events) for assessment of toxicity.

Treatment-emergent, all causality events

(a) derived from blood pressure (BP) measurement recorded monthly while on trial

(b) includes cardiovascular, cerebrovascular, and peripheral vascular ischemia

(c) includes cardiac failure, cardiac failure congestive, cardiogenic shock, cardiopulmonary failure, ejection fraction decreased, pulmonary edema, right ventricular failure

(d) includes abdominal pain, abdominal pain upper, abdominal pain lower, abdominal discomfort

(e) includes aphthous stomatitis, lip blister, mouth ulceration, oral mucosal eruption, oral pain, oropharyngeal pain, pharyngeal ulceration, stomatitis, tongue ulceration

(f) includes gastric hemorrhage, gastric ulcer hemorrhage, hemorrhagic gastritis, gastrointestinal hemorrhage, hematemesis, hematochezia, hemorrhoidal hemorrhage, intra-abdominal hemorrhage, melena, rectal hemorrhage, and upper gastrointestinal hemorrhage

(g) includes burning sensation, skin burning sensation, hyperesthesia, hypoesthesia, neuralgia, neuropathy peripheral, paresthesia, peripheral sensorimotor neuropathy, peripheral motor neuropathy, peripheral sensory neuropathy, polyneuropathy

* represents an additional 13 months of follow-up

Serious Adverse Reactions

	N (%)
Cardiovascular disorders	
Arterial ischemic event*	53 (11.8%)
Cardiovascular	28 (6.2%)
Cerebrovascular	18 (4.0%)
Peripheral vascular	16 (3.6%)
Hemorrhage	22 (4.9%)
CNS hemorrhage	10 (2.2%)
Gastrointestinal hemorrhage	10 (2.2%)
Cardiac failure*	22 (4.9%)
Effusions(a)	13 (2.9%)
Atrial fibrillation	11 (2.4%)
Venous thromboembolism	10 (2.2%)
Hypertension	8 (1.8%)
Gastrointestinal disorders	
Pancreatitis	23 (5.1%)
Abdominal pain	17 (3.8%)
Blood and lymphatic system disorders	
Febrile neutropenia	13 (2.9%)
Thrombocytopenia	13 (2.9%)
Anemia	12 (2.7%)
Infections	
Pneumonia	24 (5.3%)
Sepsis	11 (2.4%)
General	
Pyrexia	14 (3.1%)

(a) includes pericardial effusion, pleural effusion, and ascites

* represents an additional 13 months of follow-up

Laboratory Abnormalities

Myelosuppression was commonly reported in all patient populations. The frequency of grade 3 or 4 thrombocytopenia, neutropenia, and anemia was higher in patients with AP-CML, BP-CML, and Ph+ ALL than in patients with CP-CML (see Table below).

Incidence of Clinically Relevant Grade 3/4* Hematologic Abnormalities

Laboratory Test	CP-CML (N=270) (%)	AP-CML (N=85) (%)	BP-CML (N=62) (%)	Ph+ ALL (N=32) (%)
Hematology				
Thrombocytopenia (platelet count decreased)	36	47	57	47
Neutropenia (ANC decreased)	24	51	55	63
Leukopenia (WBC decreased)	14	35	53	63
Anemia (Hgb decreased)	9	26	55	34
Lymphopenia	10	26	37	22

ANC=absolute neutrophil count, Hgb=hemoglobin, WBC=white blood cell count

*Reported using NCI-CTC-AE v 4.0

Incidence of Clinically Relevant Non-Hematologic Laboratory Abnormalities

Laboratory Test	Safety Population N=449	
	Any Grade* (%)	CTCAE Grade 3/4 (%)
Liver function tests		
ALT increased	53	8
AST increased	41	4
Alkaline phosphatase increased	37	2
Albumin decreased	28	1
Bilirubin increased	19	1
Pancreatic enzymes		
Lipase increased	41	15
Amylase increased	3	<1
Chemistry		
Glucose increased	58	6
Phosphorus decreased	57	8
Calcium decreased	52	1
Sodium decreased	29	5
Glucose decreased	24	0
Potassium decreased	16	2
Potassium increased	15	2
Sodium increased	10	<1
Bicarbonate decreased	11	<1
Creatinine increased	7	<1
Calcium increased	5	0
Triglycerides increased	3	<1

ALT=alanine aminotransferase, AST=aspartate aminotransferase.

*Graded using NCI-CTC-AE v 4.0

7.3 Adverse Event Characteristics

- **CTCAE term (AE description) and grade:** The descriptions and grading scales found in the revised NCI Common Terminology Criteria for Adverse Events (CTCAE) version 4.0 will be utilized for AE reporting. All appropriate treatment areas should have access to a copy of the CTCAE version 4.0. A copy of the CTCAE version 4.0 can be downloaded from the CTEP web site http://ctep.cancer.gov/protocolDevelopment/electronic_applications/ctc.htm.

If the AE is not defined in the CTCAE, the Investigator will determine the severity of the AE based on the following definitions:

Mild (Grade 1): The AE is noticeable to the patient, but does not interfere with routine activity. The AE does not require discontinuing administration or reducing the dose of the study drug.

Moderate (Grade 2): The AE interferes with routine activity, but responds to symptomatic therapy or rest. The AE may require reducing the dose, but not discontinuing administration of the study drug.

Severe (Grade 3): The AE significantly limits the patient's ability to perform routine activities despite symptomatic therapy. In addition, the AE leads to discontinuing administration or reducing the dose of the study drug.

Life Threatening (Grade 4): The AE requires discontinuing administration of the study drug. The patient is at immediate risk of death.

Death (Grade 5): The patient dies as a direct result of the complication or condition induced by administration of the study drug.

- **Attribution of the AE:**
 - Definite – The AE is *clearly related* to the study treatment.
 - Probable – The AE is *likely related* to the study treatment.
 - Possible – The AE *may be related* to the study treatment.
 - Unlikely – The AE is *doubtfully related* to the study treatment.
 - Unrelated – The AE is *clearly NOT related* to the study treatment.

The Investigator must provide attribution for all AEs (serious and non-serious). In addition, if the investigator determines a Serious Adverse Event (SAE) is associated with trial procedures, the investigator must record this causal relationship in the source documents and on the SAE form, and report such an assessment in accordance with the SAE reporting requirements.

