Asymptomatic	Absolute decrease of >10% in LVEF compared to baseline and ejection fraction below the institution's LLN.	
 • Interrupt ponatinib and repeat ECHO within 4 weeks. • If the LVEF recovers within 4 weeks (defined as LVEF \geqLLN and absolute decrease \leq10% compared to baseline): 
 – Restart treatment with ponatinib at reduced dose by one dose level. – Repeat ECHO 4 and 12 weeks after re-start; continue in intervals of 12 weeks thereafter. • If LVEF does not recover within 4 weeks: 
 – Consult with cardiologist. – Permanently discontinue Ponatinib. – Repeat ECHO after 4, 8, 12 weeks or until resolution.
Symptomatic^b	
 • Grade 3: resting LVEF 39-20% or >20% absolute reduction from baseline • Grade 4: Resting LVEF \leq20%. 	
 • Permanently discontinue ponatinib. • Report as SAE. • Consult with cardiologist. • Repeat ECHO after 4, 8, and 12 weeks or until resolution.

^a Symptoms may include: dyspnea, orthopnea, and other signs and symptoms of pulmonary congestion and edema.

Treatment delays at the start of treatment that are unrelated to drug will require restaging of the patient and re-initiating treatment. If at any time during the course of the trial, treatment is delayed over 3 weeks due to events unrelated to drug, treatment will resume as normal once the patient is deemed stable to continue.

Dose Modifications for General Non-hematologic Toxicities

CTCAE Grade	Action and Dose Modification
-------------	------------------------------

Grade 1 or transient Grade 2	No intervention
Grade 2 lasting \geq 7 days with optimal care	Hold ponatinib Resume at 45 mg after recovery to \leq grade 1 Recurrence at 45 mg: Hold ponatinib Resume at 30 mg after recovery to \leq grade 1 Recurrence at 30 mg: Hold ponatinib Resume at 15 mg after recovery to \leq grade 1 Recurrence at 15 mg: Discontinue ponatinib
Grade 3 or 4	Hold ponatinib Resume at 30 mg after recovery to \leq grade 1 Recurrence at 30 mg: Hold ponatinib Resume at 15 mg after recovery to \leq grade 1 Recurrence at 15 mg: Discontinue ponatinib

Dose Modification for concurrent strong CYP3A inhibitors

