7.5 Serious Adverse Event Reporting Procedures

7.5.1 Serious Adverse Event Reporting Period

The Ohio State University will be solely responsible for reporting serious adverse events to the OSU IRB, FDA, and Takeda. Participating sites are only permitted to report directly to OSU and must report serious adverse events to the OSU PI and Multi-Site Coordinator within 24 hours of knowledge of the event. Serious adverse events are to be reported to the OSU IRB (per policy), FDA (per 21CFR312.32), and Takeda Drug Safety and Pharmacovigilance or its designated representative beginning from the time the patient is first administered investigational product

through and including 30 days after permanent discontinuation of the investigational product. Any SAEs occurring any time after the reporting period must be promptly reported to the OSU IRB (per policy), FDA (per 21CFR312.32) and Takeda Drug Safety and Pharmacovigilance or its designated representative if a causal relationship to the investigational product is suspected. When expedited reporting applies, OSU will provide Takeda with the submitted report of any expedited report concurrent to agency submission (no more than 1 business day/3 calendar days after the submission).

Patients must be followed for all AEs from the date the patient is first administered investigational product until at least 30 Days after the End of Treatment, and for all serious or study drug-related toxicities until the AEs are resolved or until patient contact discontinues.

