12.4 Analysis of Secondary Objectives

- Frequency and severity of adverse events and tolerability of the regimen will be collected and summarized by descriptive statistics. As per NCI CTCAE v4.0, the term toxicity is defined as adverse events that are classified as either possibly, probably, or definitely related to study treatment. The maximum grade for each type of toxicity will be recorded for each patient, and frequency tables will be reviewed to determine toxicity patterns for each of the cohorts as well as across cohorts. In addition, we will review all adverse event data that is graded as 3, 4, or 5 and classified as either “unrelated” or “unlikely to be related” to study treatment in the event of an actual relationship developing. The incidence of severe (grade 3+) adverse events or toxicities will be described. We will also assess tolerability of the regimen through

assessing the number of patients who required dose modifications and/or dose delays. In addition, we will capture the proportion of patients who go off treatment due to adverse reactions or even those who refuse further treatment for lesser toxicities that inhibit their willingness to continue participation on the trial. All patients who have received at least one dose of any of the therapeutic agent will be evaluable for toxicity and tolerability.

- Overall and Progression Free Survival as time-to-event outcomes. Kaplan-Meier curves will be used to estimate the survival distributions of overall survival and progression-free survival for each cohort. Each of these variables is measured from the date of study registration to the date of event (ie, death and/or disease progression) or the date of last follow-up if no event has occurred.
- Clinical benefit rate (CBR) at 6 months. The 6-month CBR will be calculated by the number of patients who have achieve a response and/or are progression-free and alive at 6 months divided by the total number of evaluable patients. Exact binomial 95% confidence intervals for CBR will be calculated.

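### For adverse events that CTCAE does not define, the Section 7.3 fallback scale mixes severity with dose action (Grade 3) and causality (Grade 5), so some severe or fatal events have no correct grade

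*Combined protocol and SAP*

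**What the plan says.** Section 7.3 makes CTCAE v4.0 the grading scale. It then sets a fallback: "If the AE is not defined in the CTCAE, the Investigator will determine the severity of the AE based on the following definitions". Each of fallback Grades 1 to 4 joins a clinical description to a statement about study drug:

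- Grade 2: activity is affected but the event responds to treatment of symptoms or rest. On the drug, "The AE may require reducing the dose, but not discontinuing administration of the study drug".
- Grade 3: routine activity is markedly limited despite symptomatic therapy. "In addition, the AE leads to discontinuing administration or reducing the dose of the study drug".
- Grade 4: the patient is at immediate risk of death, and the event requires that the drug be stopped.
- Grade 5: "The patient dies as a direct result of the complication or condition induced by administration of the study drug".

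The same section requires a five-level attribution for every adverse event, recorded apart from grade. Section 7.1.1 defines an adverse event without requiring a causal link. Section 7.1.2 treats as a fatal serious event "any patient death within 30 days of the last dose of study drug administration". Section 7.5.1 has adverse events followed "until at least 30 Days after the End of Treatment".

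Section 12.4 uses the grades in several ways. It tabulates the maximum grade per toxicity, describes grade 3+ incidence, and adds a check on attribution: "we will review all adverse event data that is graded as 3, 4, or 5 and classified as either" unrelated or unlikely to be related. It counts dose modifications and delays separately, as a measure of tolerability.

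**The concern.** Severity, causality and action taken are three different facts about an event. The plan collects attribution in its own field and counts dose changes in its own analysis, yet the fallback scale builds both into the grade. Two equally severe events can then be graded differently because one investigator changed the dose and another did not, or because one was thought unrelated.

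Safety and tolerability is the first secondary objective in Section 1.2, and its main summaries are grade-based. The Section 12.4 review of unrelated and unlikely grade 3-5 events exists to catch wrong attribution. A grade that itself depends on attribution, or on a dose decision that attribution influences, weakens that check for the events concerned.

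**Working it through.** The plan gives no figure to reproduce. The check sets the definitions beside the rules and analyses that use them.

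**Step 1. Which events are affected.** Only those with no CTCAE v4.0 definition. The documents give no count or expected share.

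**Step 2. The Grade 2/3 boundary.** Take a severe event that limits routine activity despite symptomatic therapy and leads to no dose change.

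| Fallback grade | Clinical part met? | Drug part met? | Grade fits? |
|---|---|---|---|
| 2 | No: it does not respond to symptomatic therapy | Yes: no discontinuation | No |
| 3 | Yes | No: the drug was neither reduced nor stopped | No |

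Grade 4 does not fit either unless the patient is at immediate risk of death. This can happen in two ordinary settings. One is the follow-up of at least 30 days after the end of treatment, when there is no dose left to change. The other is on treatment, when the event is judged unrelated and the dose is left alone; Section 7.1.1 expressly counts accidents and apparently unrelated illnesses as adverse events. The investigator must then choose a grade that the wording does not support. If Grade 2 is chosen, the event leaves both the grade 3+ incidence and the Section 12.4 review.

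**Step 3. Grade 5.** A fatal event is Grade 5 only if the condition was induced by the study drug. An event rated unrelated fails that test. So among fallback-graded events the unrelated Grade 5 cell of the Section 12.4 review is empty by definition. The toxicity tables, which count only events rated possibly related or higher, are less exposed to this clause. It matters for the all-cause incidence of grade 3+ events and for the review.

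**Step 4. Relation to Section 6.** The general non-hematologic table in Section 6.1 runs from grade to dose action. If fallback grades are entered into it, two things follow.

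- Grade and dose action depend on each other: the table needs the grade to set the action, and 7.3 needs the action to set Grade 3.
- The dose wording conflicts at two grades. At Grade 4, 7.3 says the drug must be discontinued, while the table's row for Grades 3 and 4 reads "Hold ponatinib Resume at 30 mg after recovery to" Grade 1 or lower. At Grade 2, 7.3 excludes discontinuation, while the table ends in discontinuation for a Grade 2 event lasting 7 days or more that recurs at 15 mg.

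**Step 5. Sensitivity of the summaries.** Section 12.3 plans 30 patients in Cohort A and up to 15 in Cohort B. If one patient's only grade 3+ event is misgraded, patient-level incidence moves by 1/30 = 3.3 percentage points in Cohort A, or 1/15 = 6.7 points in a full Cohort B. These are shifts per misgraded patient. They do not predict how many there will be.

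**The case against.** The strongest reply is about reach, and much of it stands.

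- **Scope.** CTCAE is the primary scale, and Section 12 defines toxicity by it. A reader might infer that the trial's grade 3-5 counts as a whole become circular with Section 6. The documents do not support that. Only events outside CTCAE are affected. The general table in Section 6.1 is headed by CTCAE grade, and nothing says that fallback grades feed into it. That table also has no Grade 5 row, so circularity cannot arise there. The point in Step 4 is conditional.
- **Deaths.** A reader might infer that the Section 12.4 review cannot see unrelated deaths. That goes too far. An on-treatment event that puts the patient at immediate risk of death and stops the drug can enter the review as Grade 4. Any death within 30 days of the last dose is a serious event whatever its cause (7.1.2). The serious-event report records severity, relationship and outcome (7.5.3), and the data and safety monitoring committee reviews serious events (7.5.9).
- **Direction.** A reader might infer that severe events after treatment are systematically under-graded. The text shows a gap in the scale, not a demonstrated downgrade; an investigator may ignore the dose clause and record Grade 3. Nor does the length of the follow-up window measure the effect, because a share of observation time is not a share of events.
- **Use.** Safety is summarised descriptively, and no numerical stopping rule or efficacy decision uses the fallback grade.
- **Wording.** The Grade 4 phrase could be read as what the event would call for and not what was done. The Grade 3 phrase is harder to read that way.

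None of this removes the two definitional faults. Followed as written, the scale gives some severe events no grade and bars unrelated deaths from Grade 5.

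**Conclusion.** The concern holds in limited form. For adverse events not defined in CTCAE v4.0, the fallback scale makes a dose change an added condition of Grade 3 and drug causation a condition of Grade 5. This is a wrong rule and not missing detail, because the plan already records attribution and counts dose changes separately, and defines adverse events and fatal serious events without regard to cause.

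The consequence is confined to grade-based summaries for that subset: grade 3+ incidence and the Section 12.4 review can miss or misgrade events. Capture of deaths as serious events under 7.1.2 is unaffected. The size cannot be estimated, since the number of fallback-graded events is not given and may be small.

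The conclusion assumes that investigators apply the wording literally. The mutual dependence of grade and dose action, and the Grade 2 and Grade 4 conflicts, rest on the further assumption that fallback grades are used in the Section 6.1 general table, which the documents leave open. The correction is worth making because it is cheap.

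**What to change.** 1. For the Section 12.4 analyses, assign fallback grades on the clinical-severity wording of Section 7.3 alone.
2. Reword fallback Grade 5 as death due to the adverse event, whatever its relationship to study drug.
3. Keep attribution, which 7.3 already requires, and action taken with study drug as separate fields on the adverse event form.
4. State whether fallback grades feed the general non-hematologic table in Section 6.1.
5. Have the sponsor reconcile the dose-action wording in 7.3, at Grades 2 and 4 in particular, with that table. This review takes no position on which dose rule is right.

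The cost is a short text change in 7.3, a sentence in 12.4 and a form instruction. No endpoint, eligibility criterion or sample size changes. The downside is that reported grade 3+ counts may rise slightly.
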